### 7.2 NCI-IRB AND CLINICAL DIRECTOR REPORTING

#### 7.2.1 NCI-IRB and NCI CD Expedited Reporting of Unanticipated Problems and Deaths

The Protocol PI will report in the NIH Problem Form to the NCI-IRB and NCI Clinical Director:

- All deaths, except deaths due to progressive disease
- All Protocol Deviations
- All Unanticipated Problems
- All non-compliance

Reports must be received within 7 days of PI awareness via iRIS.

#### 7.2.2 NCI-IRB Requirements for PI Reporting at Continuing Review

The protocol PI will report to the NCI-IRB:

1. A summary of all protocol deviations in a tabular format to include the date the deviation occurred, a brief description of the deviation and any corrective action.
2. A summary of any instances of non-compliance
3. A tabular summary of the following adverse events:
  - All Grade 2 **unexpected** events that are possibly, probably or definitely related to the research;
  - All Grade 3 and 4 events that are possibly, probably or definitely related to the research;
  - All Grade 5 events regardless of attribution;
  - All Serious Events regardless of attribution.

**Abbreviated Title:** Ph II Sunitinib CNS Sarcomas  
**Version Date:** 05-30-18

**NOTE:** Grade 1 events are not required to be reported.

### **7.3 SAFETY REPORTING CRITERIA TO THE PHARMACEUTICAL COLLABORATORS**

#### **7.3.1 Reporting of Serious Adverse Events**

Within twenty-four (24) hours of first awareness of the event (immediately if the event is fatal or life-threatening), Principal Investigator will report to Pfizer by facsimile at [name] any Serious Adverse Event (“SAE.”). Such SAEs are to be reported for (1) Study subjects who are assigned or (2) individuals otherwise exposed to the Pfizer Product. Principal Investigator should report SAEs as soon as they are determined to meet the definition, even if complete information is not yet available.

#### **7.3.2 Pregnancy: Exposure or Lack of Effect**

Even though there may not be an associated SAE, exposure to the Pfizer Product during pregnancy, exposure to the Pfizer Product during lactation, and occupational exposure to the Pfizer Product are reportable, and lack of effect of the Pfizer Product may also be reportable. The term SAE will be understood to include exposure during pregnancy, exposure during lactation, occupational exposure, and reportable instances of lack of effect.

#### **7.3.3 Hy’s Law Cases**

Cases of potential drug-induced liver injury as assessed by laboratory test values (“Hy’s Law Cases”) are also reportable to Pfizer. If a Study subject develops abnormal values in aspartate aminotransferase (“AST”) or alanine aminotransferase (“ALT”) or both, concurrent with abnormal elevations in total bilirubin and no other known cause of liver injury, that event would be classified as a Hy’s Law Case. The term SAE will be understood to also include Hy’s Law Cases.

#### **7.3.4 Reporting**

##### **7.3.4.1 Forms**

Principal Investigator will report SAEs using one of the following forms: (1) a reporting form approved by the local regulatory authority, (2) a CIOMS form, (3) a Pfizer-provided *Investigator-Initiated Research Serious Adverse Event Form*, or (4) any other form prospectively approved by Pfizer. The *Reportable Event Fax Cover Sheet* provided by Pfizer must also be included with each SAE submitted.

##### **7.3.4.2 SAE Reporting Period**

The SAEs that are subject to this reporting provision are those that occur from after the first dose of the Pfizer Product through twenty-eight (28) calendar days after the last administration of the Pfizer Product. In addition, if Principal Investigator becomes aware of an SAE occurring any time after the administration of the last dose of the Pfizer Product, Principal Investigator should report that SAE to Pfizer if the Principal Investigator suspects a causal relationship between the Pfizer Product and the SAE.

##### **7.3.4.3 Exclusions from SAE Reporting Requirements**

Specifically excluded from the reporting requirements for SAEs under this protocol is any SAE identified in the Protocol as anticipated to occur in the Study population at some frequency independent of drug exposure, unless the Principal Investigator assesses such an event as related

*Abbreviated Title:* Ph II Sunitinib CNS Sarcomas

*Version Date:* 05-30-18

to the Pfizer Product. Also, specifically excluded from the reporting requirements is any SAE judged by the Principal Investigator to represent progression of the malignancy under study, unless it results in death within the SAE Reporting Period.

## 7.4 DATA AND SAFETY MONITORING PLAN

### 7.4.1 Principal Investigator/Research Team

The clinical research team will meet on a weekly basis when patients are being actively treated on the trial to discuss each patient. Decisions about dose level enrollment and dose escalation if applicable will be made based on the toxicity data from prior patients.

All data will be collected in a timely manner and reviewed by the principal investigator or a lead associate investigator. Adverse events will be reported as required above. Any safety concerns, new information that might affect either the ethical and or scientific conduct of the trial, or protocol deviations will be immediately reported to the IRB using iRIS.

The principal investigator will review adverse event and response data on each patient to ensure safety and data accuracy. The principal investigator will personally conduct or supervise the investigation and provide appropriate delegation of responsibilities to other members of the research staff.

## 8 STATISTICAL CONSIDERATIONS

### 8.1 GENERAL APPROACH

We monitor the ORR using the Bayesian optimal phase 2 (BOP2) design [18]. Specifically, let  $n$  denote the interim sample size and  $N$  denote the maximum sample size. Let  $p$  denote the ORR and define the null hypothesis  $H_0: p \leq 0.2$ , representing that the treatment is ineffectual. We will stop enrolling patients and claim that the treatment is not promising if

$$Pr(p > 0.2 | data) < \lambda \left(\frac{n}{N}\right)^\alpha,$$

where  $\lambda=0.85$  and  $\alpha=0.8$  are design parameters optimized to minimize the chance of incorrectly claiming that an efficacious treatment is not promising (i.e., type II error) under the alternative hypothesis  $H_1: p = 0.4$ , while controlling the type I error rate at 0.1 (i.e., the chance of incorrectly claiming that an ineffectual treatment is promising is no more than 10%).

Assuming a Beta(0.2,0.8) prior distribution for  $p$ , the above decision rule corresponds to the following stopping boundaries and yields a statistical power of 0.8537 under  $H_1$ :

**Table 1.** Stopping boundaries

# patients treated	Stop if # responses <=
16	3
24	5
32	9

Based on Table 1, we perform the interim and final analysis when the number of enrolled patients reaches 16, 24 and 32. If the number of responses fails to exceed the stopping boundary, we will suspend accrual, inspect the efficacy data and make the go/no-go decision based on both the ORR and other clinical considerations (e.g., PFS).

*Abbreviated Title: Ph II Sunitinib CNS Sarcomas*

*Version Date: 05-30-18*

Below are the operating characteristics of the design based on 10000 simulations using the BOP2 web application, which is available at <http://www.trialdesign.org>.

ORR	Early stopping (%)	Claim promising (%)	Sample size
0.1	97.95	0.05	16.7
0.2	71.74	8.00	21.5
0.3	31.45	46.22	27.5
0.4	7.92	85.37	30.8
0.5	1.31	98.13	31.8

We monitor the rate of Dose Limiting Toxicity (DLT) independently for each cohort using the following Bayesian rule: stop enrolling patients to a cohort if  $\text{Pr}(\text{DLT} > 30\% \mid \text{data}) > 0.9$ . That is, we will stop enrolling patients to a cohort if the data indicate that there is more than 90% chance that the true DLT rate is higher than 30%. This posterior probability is calculated based on the beta-binomial model. The decision rule gives the following stopping rule, assuming a Beta(0.1, 0.4) prior distribution for DLT rate,

Stop enrolling pts if  $[\# \text{ of pts with DLT}] / [\# \text{ of pts evaluated}] \geq 4/5, 6/10, \text{ and } 9/20$ .

Below are the operating characteristics of the toxicity monitoring rule:

		True toxicity rate				
		0.1	0.2	0.3	0.4	0.5
Early stop probability	0.008	0.018	0.145	0.440	0.771	
Average sample size	31.9	31.6	29.4	24.4	17.7	

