## 8.2 SAMPLE SIZE JUSTIFICATION

With the maximum sample size of 32 patients per cohort, the 95% confidence interval of the estimated ORR will not be wider than 0.19 in each direction. At the two-sided significance level of 0.2, we have 80% power to detect the ORR of 48% versus 30%.

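### Does the DLT stopping rule leave its look schedule undefined, with no boundary after patient 20 of a 32-patient cohort?

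*Combined protocol and SAP*

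**What the plan says.** Section 8.1 sets the scope first: "We monitor the rate of Dose Limiting Toxicity (DLT) independently for each cohort using the following Bayesian rule". The criterion is a posterior probability above 0.9 that the DLT rate is greater than 30%, under a beta-binomial model with a Beta(0.1, 0.4) prior. In words, "we will stop enrolling patients to a cohort if the data indicate that there is more than 90% chance that the true DLT rate" is above that level. The text then continues "The decision rule gives the following stopping rule" and gives the boundaries as patients with DLT over patients evaluated: at least 4/5, 6/10 and 9/20. A table introduced by "Below are the operating characteristics of the toxicity monitoring rule" gives early-stop probability and average sample size at true rates 0.1 to 0.5.

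Section 8.2 gives the cohort ceiling: "With the maximum sample size of 32 patients per cohort". For response, Section 8.1 states its looks in a sentence: "we perform the interim and final analysis when the number of enrolled patients reaches 16, 24 and 32". The DLT rule has no matching sentence.

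**The concern.** A stopping rule needs both a criterion and the times at which it is applied. The DLT criterion is worded without times, and the listed boundaries end at 20. For patients 21 to 31 no boundary is listed, yet the worded criterion can still be met. The posterior probability is 0.921 at 11/25 and 0.931 at 13/30. A cohort that passes the last look at 8/20 (0.809) would meet the criterion at 10/21 (0.948) without meeting any listed boundary.

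If the two statements were rival rules, the same data could lead to different enrolment decisions, and the published error rates would describe only one of them. In a safety rule that would matter. The response rule states its looks in words, which makes the omission for DLT more noticeable.

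**Working it through.** **Inputs.** Prior Beta(0.1, 0.4), threshold 0.30, cut-off 0.9, boundaries 4/5, 6/10 and 9/20, and the published table (all Section 8.1). Maximum 32 per cohort (Section 8.2). DLT status is assumed known at each look, and efficacy stops are ignored until step 4.

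**1. Boundaries.** With x DLTs in n patients the posterior is Beta(0.1 + x, 0.4 + n − x). Its tail above 0.3 is:

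| n | listed boundary | one fewer DLT |
|---|---|---|
| 5 | 4: 0.986 | 3: 0.897 |
| 10 | 6: 0.970 | 5: 0.890 |
| 20 | 9: 0.910 | 8: 0.809 |

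All three listed boundaries are the smallest counts that exceed 0.9.

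**2. Published operating characteristics.** These are computed by exact binomial recursion, stopping only at 5, 10 and 20. At a true rate of 0.3:

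- The chance of stopping at 5 is 5 × 0.3⁴ × 0.7 + 0.3⁵ = 0.0308.
- The chance of a first stop at 10 is 0.0320, and at 20 it is 0.0770.
- The total is 0.0308 + 0.0320 + 0.0770 = 0.140 (rounded).
- The average n is 5 × 0.0308 + 10 × 0.0320 + 20 × 0.0770 + 32 × 0.8603 = 29.54.

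| True rate | Early stop, exact | published | Average n, exact | published |
|---|---|---|---|---|
| 0.1 | 0.0006 | 0.008 | 31.98 | 31.9 |
| 0.2 | 0.0184 | 0.018 | 31.63 | 31.6 |
| 0.3 | 0.1397 | 0.145 | 29.54 | 29.4 |
| 0.4 | 0.4368 | 0.440 | 24.39 | 24.4 |
| 0.5 | 0.7670 | 0.771 | 17.79 | 17.7 |

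If this table also used 10,000 simulations (the number given for the response table, so an assumption here), the simulation standard errors at 0.3, 0.4 and 0.5 are 0.0035, 0.0050 and 0.0042. The differences of 0.005, 0.003 and 0.004 are within about 1.5 of these.

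**3. Other schedules fit worse.**

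- Checking after every patient gives 0.311 at a true rate of 0.3, against 0.145 published.
- Adding a look at 30 gives 0.529 and 0.867 at rates 0.4 and 0.5, against 0.440 and 0.771.
- Adding a look at 15 gives similar stop probabilities (0.442 and 0.770), but the average n falls to 23.93 and 16.99, against 24.4 and 17.7.

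Of the schedules tried, 5, 10 and 20 alone is the one that matches both rows at rates 0.2 to 0.5.

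**4. What later looks would add.** The same prior and cut-off give at least 11/25 and 13/30. A stop at 25 saves 32 − 25 = 7 patients and a stop at 30 saves 2. At a true rate of 0.4 the added stop probabilities are 0.0653 and 0.0446, so the saving is 7 × 0.0653 + 2 × 0.0446 = 0.55 patient.

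| True rate | Early stop, 5/10/20 | with 25 and 30 added | Patients saved |
|---|---|---|---|
| 0.2 | 0.018 | 0.021 | 0.01 |
| 0.3 | 0.140 | 0.175 | 0.18 |
| 0.4 | 0.437 | 0.547 | 0.55 |
| 0.5 | 0.767 | 0.876 | 0.55 |

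The response rule shrinks this further. Suppose every suspension at 16 or 24 ends accrual and response is independent of DLT. At a DLT rate of 0.4 the average n then falls from 17.88 to 17.72 at ORR 0.2, from 21.65 to 21.27 at ORR 0.3, and from 23.68 to 23.18 at ORR 0.4. The savings are 0.16, 0.38 and 0.50 patient.

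**5. The 0.1 column.** The published early-stop probability of 0.008 is about 13 times the exact 0.0006 (0.008 / 0.0006 = 13.3), and the average of 31.9 should round to 32.0. Both early-stop values are below 1%.

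**The case for a change.** The strongest case for a change is that a safety stopping rule should not have to be inferred. The worded criterion carries no time limit. The phrase that introduces the list could be read as giving examples from a continuously applied criterion. A reader has to rebuild the table to be sure otherwise. A team looking at 11/25 could feel bound by the wording and unbound by the list, and one sentence would settle it.

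Part of this stands. No sentence says that the criterion is applied at 5, 10 and 20 only, and one would be tidy. But the criterion and the boundaries form one continuous statement, with the denominators labelled as patients evaluated, so the sample sizes are on the page. The sentence would record what the list and its table already show. It would move no boundary and no error rate.

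Patients 21 to 31 are not unwatched either. Section 7.4.1 states: "The clinical research team will meet on a weekly basis when patients are being actively treated on the trial to discuss each patient". The same section provides for review of adverse events by the principal investigator and for immediate reporting of safety concerns to the IRB. If too few responses are seen at 24 patients, Section 8.1 says "we will suspend accrual, inspect the efficacy data and make the go/no-go decision". These are not pre-specified DLT boundaries, but they limit what the missing sentence could cost.

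Adding later looks is a different proposal. It trades about half a patient per cohort at rates of 0.4 to 0.5 for more stopping at 0.2 and 0.3. Three early looks are a legitimate choice, and the published table shows that the sponsor evaluated them.

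**Conclusion.** No change to the plan follows. The missing sentence is a drafting gap that a competent analyst fills correctly: the listed boundaries follow from the stated prior and cut-off, and looks at 5, 10 and 20 reproduce the published characteristics at true rates 0.2 to 0.5 to within 0.006 in probability and 0.15 in average n. A team that follows the list gets the properties the protocol reports. The absence of a listed boundary after patient 20 is a fair trade-off, worth at most about 0.55 patient per cohort for looks at 25 and 30, and less once the response stops are counted. The 0.1 column is a clerical slip with no consequence for any decision.

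This rests on DLT status being known when each look is taken. The response-adjusted figures also assume that suspension ends accrual and that response and DLT are independent.

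### The early stop probability printed for a 10% true DLT rate (0.008) does not follow from the stated toxicity rule; the exact value is 0.0006

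*Combined protocol and SAP*

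**What the plan says.** Section 8.1 (General Approach) monitors dose-limiting toxicity "independently for each cohort". Enrolment to a cohort stops when the data indicate "more than 90% chance that the true DLT rate is higher than 30" percent, "assuming a Beta(0.1, 0.4) prior distribution for DLT rate". The plan converts this into count boundaries, introduced by "Stop enrolling pts if": at least 4 of 5, 6 of 10, or 9 of 20 evaluated patients with a DLT. Section 8.2 sets a "maximum sample size of 32 patients per cohort".

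A table of operating characteristics follows the boundaries. Under the header "True toxicity rate" it has five columns and two rows:

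| Row | 0.1 | 0.2 | 0.3 | 0.4 | 0.5 |
|---|---|---|---|---|---|
| "Early stop probability" | 0.008 | 0.018 | 0.145 | 0.440 | 0.771 |
| "Average sample size" | 31.9 | 31.6 | 29.4 | 24.4 | 17.7 |

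The 10,000 simulations mentioned in Section 8.1 are stated for the response-rate table. No run count or method is given for the toxicity table.

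**The concern.** The first entry looks too large beside its neighbour. At a true rate of 0.1, four or more DLTs in five patients is a very rare event, and the later boundaries are harder still to reach. Yet the table shows the stop probability only a little more than doubling, from 0.008 to 0.018, when the true rate doubles from 0.1 to 0.2.

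The plan gives no other operating characteristics for the toxicity rule. The 0.1 column is its most direct statement of how often a clearly tolerable cohort would be closed by mistake. A reviewer who recomputes that entry from the plan's own inputs will not reproduce it, and may then doubt a rule that is otherwise correctly derived.

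**Working it through.** **Inputs.** From Section 8.1: stop if Pr(DLT rate > 0.30 | data) > 0.90; Beta(0.1, 0.4) prior; looks at n = 5, 10 and 20 with boundaries 4, 6 and 9; true rates 0.1 to 0.5. From Section 8.2: maximum n = 32 per cohort.

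**Step 1: do the boundaries follow from the prior and threshold?** With r DLTs in n patients the posterior is Beta(0.1 + r, 0.4 + n − r). Its probability above 0.30 is:

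| n | one DLT below the boundary | at the boundary |
|---|---|---|
| 5 | 3/5: 0.897 | 4/5: 0.986 |
| 10 | 5/10: 0.890 | 6/10: 0.970 |
| 20 | 8/20: 0.809 | 9/20: 0.910 |

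Each printed boundary is the smallest count that passes 0.90, so the rule is read correctly.

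**Step 2: exact operating characteristics.** At each look, the probability of stopping is the binomial probability of reaching the boundary, carried forward only over paths that have not already stopped. The average sample size is the sum of (n at stopping × probability of stopping there) plus 32 × (probability of never stopping).

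At a true rate p = 0.1:

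- n = 5: P(X ≥ 4) = 5 × 0.1⁴ × 0.9 + 0.1⁵ = 0.00045 + 0.00001 = 0.00046.
- n = 10: the sum over k = 1, 2, 3 of P(k DLTs in the first 5) × P(at least 6 − k in the next 5) = 0.328 × 0.00001 + 0.0729 × 0.00046 + 0.0081 × 0.00856 = 0.00011.
- n = 20: the same recursion over the next 10 patients gives 0.00005.
- Total: 0.00061 (unrounded terms).
- Average sample size: 32 − (27 × 0.00046 + 22 × 0.00011 + 12 × 0.00005) = 31.98.

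Across all five rates:

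| True rate | Stop probability, printed | Stop probability, exact | Average n, printed | Average n, exact |
|---|---|---|---|---|
| 0.1 | **0.008** | **0.0006** | 31.9 | 31.98 |
| 0.2 | 0.018 | 0.0184 | 31.6 | 31.63 |
| 0.3 | 0.145 | 0.1397 | 29.4 | 29.54 |
| 0.4 | 0.440 | 0.4368 | 24.4 | 24.39 |
| 0.5 | 0.771 | 0.7670 | 17.7 | 17.79 |

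The stop probabilities at 0.2 to 0.5 are within about 1.5 standard errors of the exact values if 10,000 runs are assumed, and within about 0.5 if 1,000 are. Only the 0.1 entry fails: 0.008 / 0.00061 is about 13, an absolute gap of about 0.0074.

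**Step 3: could this be simulation error?** The run count is not stated, so a range is shown. The standard error is √(0.00061 × 0.99939 / runs).

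- 1,000 runs: standard error 0.00078; gap 0.0074 / 0.00078, about 9 standard errors. About 0.6 stops would be expected, and 8 or more has probability of about 3 × 10⁻⁷.
- 10,000 runs: standard error 0.00025; about 30 standard errors.

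**Step 4: would another reading of the rule give 0.008?** None of those tried does so while keeping the rest of the row.

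| Variant | Rate 0.1 | Rate 0.2 | Rate 0.3 |
|---|---|---|---|
| Printed | 0.008 | 0.018 | 0.145 |
| First boundary 3/5 | 0.0086 | 0.065 | 0.228 |
| Second boundary 5/10 | 0.0019 | 0.039 | 0.200 |
| Third boundary 8/20 | 0.0009 | 0.038 | 0.241 |
| Extra look at 30, stop at 13 | 0.0006 | 0.020 | 0.165 |
| Strictly above the boundaries | 0.00002 | 0.003 | 0.053 |

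Continuous monitoring, started at patient 1, 3, 5 or 10, gives 0.0006 to 0.0136 at rate 0.1 but 0.031 to 0.086 at 0.2.

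**The case against.** The strongest objection is that the error hardly matters. Both figures are near zero, and the 13-fold ratio compares two very small numbers. Nobody would judge the rule differently at 0.8% than at 0.06%. The printed value overstates false stopping, and the 0.2 column, also below the 30% limit, is correct. All of this stands and keeps the point minor. It does not make the entry right: the plan states an operating characteristic that its rule does not have.

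A reader might infer that the 0.1 column was computed for a different scenario, since a stop probability of 0.008 corresponds to a true rate of about 17%. The documents do not support that. A one-cell slip fits at least as well: 0.0008, for example, would lie within one standard error of 0.00061 if 10,000 runs are assumed. At 17% the exact average sample size is 31.83, which rounds to 31.8 and not the printed 31.9, although simulation error could bridge that difference. Neither cause can be established.

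A reader might also treat the whole column as wrong. The sample-size gap, 31.9 against 31.98, is under 0.1 patient and could be truncation or, with few runs, noise. The clear failure is one cell.

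Finally, the table's layout is imperfect in the extracted text, so a misread digit cannot be wholly excluded. Against that, each row has five values in order, and four of the five stop probabilities match their labels. A glance at the source page would settle it.

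**Conclusion.** The point holds for one cell. The early stop probability at a true DLT rate of 0.1 should be 0.0006, not 0.008; the printed value overstates false stopping by about 0.7 percentage points. This rests on the plan's own boundaries, looks at 5, 10 and 20 patients, and a maximum of 32 per cohort, a reading that the other four stop probabilities confirm. It does not depend on the unstated number of simulation runs. The documents do not identify the cause. The finding is no evidence of a fault in the toxicity rule: the prior, the 0.90 threshold, the boundaries and the sample size all stand. It is a minor correction to the reported figures, with no consequence for trial conduct.

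**What to change.** In the toxicity table of Section 8.1, replace 0.008 with 0.0006 (0.001 if three decimals are kept). For consistency, change the average sample size in the same column from 31.9 to 32.0. No other cell needs to change, and the table need not be re-run. The cost is two numbers in one table, with no change to the design.

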## 8.2 SAMPLE SIZE JUSTIFICATION

With the maximum sample size of 32 patients per cohort, the 95% confidence interval of the estimated ORR will not be wider than 0.19 in each direction. At the two-sided significance level of 0.2, we have 80% power to detect the ORR of 48% versus 30%.

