## 8.3 STATISTICAL ANALYSIS

Summary statistics, including mean, standard deviation and 95% confidence interval, will be used to describe the ORR. Kaplan-Meier curve will be used to estimate the PFS. We will calculate mean, standard deviation and 95% confidence interval of PFS6 and median PFS. Safety will be assessed by reporting the grades of toxicity and the type of toxicity observed for all patients and summarizing data using the descriptive statistics, including mean, standard deviation and confidence intervals.

*Abbreviated Title: Ph II Sunitinib CNS Sarcomas*

*Version Date: 05-30-18*

Treatment effect of sunitinib will be evaluated using advanced MRI of the brain. Perfusion and diffusion-based MRI parameters including but not restricted to blood volume, mean and median ADC and structural volumes will be analyzed. Results will be summarized, and mean and median values at different time points will be tabulated. Changes in such parameters will be checked for statistical significance and correlated with the disease status. The relationship between biomarkers and response will be evaluated using Spearman correlation and regression analysis; the levels of biomarkers will be compared between responders and non-responders using an exact Wilcoxon rank sum test and t test.

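### The power statement in Section 8.2 (ORR 48% versus 30%) does not describe the 20% versus 40% design specified in Section 8.1

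*Combined protocol and SAP*

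**What the plan says.** Section 8.2 gives two supports for a maximum of 32 patients per cohort. The first is precision: "the 95% confidence interval of the estimated ORR will not be wider than 0.19 in each direction". The second is power: "At the two-sided significance level of 0.2, we have 80% power to detect the ORR of 48% versus 30" percent. It names no test, gives no reason for either rate, and does not mention the rule in 8.1.

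Section 8.1 specifies a Bayesian optimal phase 2 (BOP2) rule for the ORR. The null is an ORR of 0.2 or less, "representing that the treatment is ineffectual", and the alternative is 0.4. The design parameters are chosen to maximize power "while controlling the type I error rate at 0.1", and the rule "yields a statistical power of 0.8537 under" the alternative. On timing, "we perform the interim and final analysis when the number of enrolled patients reaches 16, 24 and 32". The stopping boundaries are 3, 5 and 9 responses or fewer, so a cohort is promising with at least 10 responses in 32.

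Section 8.3 plans only description of the ORR: "Summary statistics, including mean, standard deviation and 95% confidence interval, will be used to describe the ORR".

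**The concern.** The two sections describe the same 32 patients with different null rates (30% and 20%), different alternatives (48% and 40%) and different power (80% and 85.37%). Section 8.2 is where a reader looks to learn what 32 patients per cohort can show. As written, it suggests that 30% is the rate to beat. Under the rule that will actually be applied, a drug with a true ORR of 30% is called promising almost half the time. ORR is the primary endpoint, so anyone reviewing the design or interpreting a cohort's result needs a single benchmark.

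**Working it through.** **Inputs.** From 8.1: null 0.20, alternative 0.40, Beta(0.2, 0.8) prior, λ = 0.85, exponent 0.8, looks at 16/24/32, stop at ≤3, ≤5, ≤9. From 8.2: n = 32, rates 0.30 and 0.48, two-sided level 0.2, power 80%, confidence-interval (CI) arm 0.19.

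**1. The 80% in 8.2.** Assume a single-stage, one-sample normal-approximation test; this is inferred, since 8.2 names none. The upper tail of two-sided 0.2 is 0.10, so z = 1.2816.

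- Power = Φ[(0.18·√32 − 1.2816·√(0.30·0.70)) / √(0.48·0.52)] = Φ[(1.0182 − 0.5873) / 0.4996] = Φ(0.863) = **0.806**
- Required n = [(1.2816·√0.21 + 0.8416·√0.2496) / 0.18]² = **31.3**, which rounds up to 32

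The figure therefore has a clear source, but it depends on the method. An exact binomial test with upper tail at most 0.10 against 30% needs 14/32 (tail 0.069; 13/32 would give 0.133), and its power at 48% is 0.744.

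**2. The 8.1 boundaries.** The rule stops when Pr(p > 0.2 | data) < 0.85·(n/32)^0.8.

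| n | Threshold | Posterior at boundary | Posterior at one response more |
|---|---|---|---|
| 16 | 0.488 | 3 responses: 0.401 | 4: 0.644 |
| 24 | 0.675 | 5 responses: 0.501 | 6: 0.691 |
| 32 | 0.850 | 9 responses: 0.846 | 10: 0.923 |

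Boundaries 3, 5 and 9 reproduce.

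**3. What the 8.1 rule does at each rate.** Exact binomial enumeration over the three looks, treating the boundaries as binding:

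| True ORR | Promising, exact | Promising, 8.1 table | Implied by the 8.2 sentence |
|---|---|---|---|
| 20% | 0.0807 | 8.00% | – |
| 30% | 0.4700 | 46.22% | 10% |
| 40% | 0.8555 | 85.37% | – |
| 48% | 0.9707 | not tabulated | 80% |

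The exact values agree with the protocol's simulated table, so 8.1 is internally sound. The rule reaches 80% power at an ORR of about 38%. Dropping the interim looks does not recover the 8.2 figures: at least 10/32 at a single look has probability 0.505 at 30%.

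**4. The CI sentence.** Over all possible x/32, the largest distance from the estimate to a 95% Clopper–Pearson limit is 0.188, at 11/32 = 0.344 (interval 0.186 to 0.532). The largest Wald half-width is 1.96·√(0.25/32) = 0.173. Both are within 0.19.

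**The case against.** The best defence is that 8.2 never attributes the 80% to the BOP2 rule. Section 8.1 presents that rule as monitoring, and both sentences of 8.2 can be read as supplementary fixed-sample descriptions of what 32 patients offer. The CI sentence ignores the looks too, and it is not faulted. On that reading the arithmetic is right and only a label is missing. The reading is weak because nothing marks the sentence as an illustration. It states a power in the present tense under the sample-size heading, and no planned analysis uses 30%. The CI sentence differs in that 8.3 does plan a 95% interval.

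Several narrower points stand:

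- The error levels agree: the upper tail of two-sided 0.2 is the 0.1 of 8.1.
- The looks matter little. Imposing the ≤3/16 and ≤5/24 stops on a final test against 30% lowers power at 48% only from 0.744 to 0.743 (cut 14/32) or from 0.844 to 0.842 (cut 13/32). The substantive conflict is the pair of rates.
- The 46–47% at an ORR of 30% is not a type I error under the 8.1 null. A rate midway between null and alternative should give an intermediate probability, and 8.1 prints it openly.
- Section 1.2.4 (Past Experience) is not in the text available for review, so an explanation of 30% or 48% there cannot be excluded. Such an explanation would not make the 8.2 power a property of the 8.1 rule; it would raise the question of why 8.1 uses 20%.

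**Conclusion.** The concern holds, as an inconsistency that should be corrected. The 80% is sound arithmetic for a test the plan does not contain. At 30% and 48% the planned rule gives about 0.47 and 0.97, against the 0.10 and 0.80 implied by 8.2. Two assumptions underlie these figures: that 8.2 used a fixed-sample normal approximation, and that the 8.1 boundaries bind. In fact 8.1 lets the go/no-go decision after a boundary is met also weigh other clinical considerations such as PFS. Neither assumption is needed to see the mismatch, because the 46.22% in the protocol's own table shows it. The finding does not imply that 32 patients are too few; the precision statement and the 8.1 operating characteristics both still support that number.

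**What to change.** Keep the CI sentence in 8.2. Delete the 48% versus 30% sentence and cite instead the 8.1 operating characteristics for 32 patients per cohort: probability of being declared promising 8.00% at an ORR of 20%, 46.22% at 30% and 85.37% at 40%. This is one sentence of protocol wording, with no change to sample size, boundaries or conduct.

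If the sponsor wants to keep the calculation, label it as a separate fixed-sample illustration, name the test and justify both rates. If 30% is in fact the rate regarded as uninteresting, say so with reasons and recompute the 8.1 boundaries and table against it. That is a larger change, and nothing in the text available indicates that it is intended.
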